7 STATISTICAL METHODOLOGY

7.1 General Considerations

For continuous variables, descriptive statistics will include the number of subjects (n), mean, standard deviation, median, minimum and maximum. When needed, the use of other percentiles (e.g., 10%, 25%, 75% and 90%) will be mentioned in the relevant section. Frequencies and percentages will be displayed for categorical data. Percentages by categories will be based on the number of subjects with no missing data, i.e. will add up to 100%. Kaplan-Meier survival curves will be displayed for time-to-event variables and median survival time will be estimated with 2-sided 95% confidence interval (CI).

Summaries based on FAS and PPS (e.g. disposition, baseline and efficacy data) will be presented by planned treatment, unless specifically stated otherwise. Safety analysis and other summaries based on SAF, PKAS or PDAS will be presented by actual treatment received.

All statistical comparisons will be made using one sided test at the α =0.025 significance level unless specifically stated otherwise. All null hypotheses will be Arm A is not better than Arm B, all alternative hypotheses will be Arm A is better than Arm B, unless specifically stated otherwise.

All data processing, summarization, and analyses will be performed using SAS® Version 9.2 or higher on Unix. Specifications for table, figure, and data listing formats can be found in the TLF specifications for this study.

Study day for safety assessments (e.g. laboratory assessment, onset of adverse events, vital signs, etc.) will be calculated in reference to the first dose date. For assessments conducted before the first dose, study day will be calculated as (assessment date – first dose date). For assessments conducted on or after the first dose, study day will be calculated as (assessment date – first dose date \pm 1).

Study day for efficacy assessments (imaging assessment, overall survival, tumor response, etc.) will be calculated in reference to the randomization date. For assessments conducted before randomization, study day will be calculated as (assessment date – randomization date). For assessments conducted on or after randomization, study day will be calculated as (assessment date – randomization date + 1).

For efficacy evaluation, baseline is defined as the last available measurement before randomization. For safety evaluation, baseline is defined as the last available measurement before first dose. Unless otherwise specified, all summaries will be presented by treatment arm.

For the definition of subgroups of interest please refer to Section 7.8

7.2 Study Population

7.2.1 Disposition of Subjects

The following subject data will be presented:

- Number and percentage of subjects with informed consent, discontinued before randomization, randomized (overall only);
- Number and percentage of subjects randomized in each analysis set, by treatment group and overall;
- Number and percentage of subjects discontinued treatment, by primary reason for treatment discontinuation, by treatment group for FAS and SAF;
- Number and percentage of subjects completed the 30 day follow-up visit, by primary reason for 30 day follow-up discontinuation for randomized subjects, by treatment group;
- Number and percentage of subjects completed or discontinued post-treatment period, by primary reason for post-treatment discontinuation for randomized subjects, by treatment group;
- Number and percentage of subjects completed or discontinued long term follow-up period, by primary reason for long term follow-up discontinuation for randomized subjects, by treatment group;
- Number and percentage of subjects completed or discontinued survival follow-up period, by primary reason for survival follow-up discontinuation for randomized subjects, by treatment group;
- Number and percentage of screen failure subjects, by primary reason for screen failure for screen failure subjects only;
- Number and percentage of subjects excluded from PPS by reason for exclusion defined in Section 5.2.1 by treatment arm for FAS.

Sponsor: Astellas Pharma Global Development, Inc.

ISN/Protocol 8273-CL-0302

7.2.2 Protocol Deviations

Protocol deviations as defined in the study protocol (Section 8.1.6 Protocol Deviations) will be assessed for all subjects randomized. The number and percentage of subjects meeting any criteria will be summarized for each criterion and overall, by treatment group and overall as well as by study site. Subjects deviating from a criterion more than once will be counted once for the corresponding criterion. Any subjects who have more than one protocol deviation will be counted once in the overall summary. A data listing will be provided by site and subject.

The protocol deviation criteria will be uniquely identified in the summary table and listing. The unique identifiers will be as follows:

- PD1 Entered into the study even though they did not satisfy entry criteria,
- PD2 Developed withdrawal criteria during the study and was not withdrawn,
- PD3 Received wrong treatment or incorrect dose,
- PD4 Received excluded concomitant treatment.

7.2.3 Demographic and Other Baseline Characteristics

Demographic and other baseline characteristics will be summarized by descriptive statistics.

Number and percentage of subjects randomized in each country and site will be presented by treatment group and overall for the FAS.

Descriptive statistics for age, weight, body mass index (BMI) and height at study entry will be presented. Frequency tabulations for sex, ethnicity, age group (defined in Section 7.8) and race will be presented. Stratification factors (ECOG performance status, TKI chosen, Race and EGFR status) used at randomization will also be summarized by treatment group and overall. In addition, summary statistics for tobacco history and number of pack years will also be presented. This will be done for SAF, FAS, PPS, PKAS and PDAS by treatment group and overall.

Frequency tabulations for NSCLC disease history (primary diagnosis, most recent NSCLC stage, primary tumor stage, regional lymph node stage and distant metastasis) as well as the descriptive statistics for duration of disease (duration since initial diagnosis and duration since date of locally advanced or metastatic disease diagnosis) will be provided by treatment group and overall for FAS and SAF.

EGFR and T790 status (exon 19 deletion, exon 21 L858R and T790M mutation status) from local and central assessments will be summarized separately by treatment group and overall for FAS and SAF.

Medical history other than NSCLC and conditions existing at Baseline will be coded in MedDRA and summarized by System Organ Class (SOC) and Preferred Term (PT) as well as by PT alone, by treatment group and overall for the FAS. Baseline conditions are defined as those ongoing at the time of informed consent or arise following the time of informed

consent and before the first dose of study drug. For ongoing medical conditions, Common Terminology Criteria for Adverse Events (CTCAE) grade will be provided in listing.

7.2.4 Previous and Concomitant Medications

Previous medications are coded with WHO-DD, and will be summarized by therapeutic subgroup (ATC 2nd level) ,chemical subgroup (ATC 4th level) , preferred WHO name and route for the SAF.

As with previous medication, concomitant medication will be summarized for each treatment group by therapeutic subgroup (ATC 2nd level) ,chemical subgroup (ATC 4th level) ,preferred WHO name and route for the SAF. Subjects taking the same medication multiple times will be counted once per medication and investigational period. All previous and concomitant medications will be coded by indication-specific ATC.

7.2.5 Prior Anti-Cancer Drug Therapy for NSCLC

Frequency tabulations of subjects with prior NSCLC drug therapy and best response to prior drug therapy will be presented by treatment group and overall for FAS.

7.2.6 Prior Radiation Therapy

Frequency tabulations of subjects with prior radiation therapy will be presented by treatment group and overall for FAS.

7.2.7 Prior Cancer Surgical Procedures

Frequency tabulations of subjects with prior cancer surgical procedures will be presented by treatment group and overall for FAS.

7.2.8 Previous and Concomitant Non-Medication Therapy

Frequency tabulations of subjects with previous and non-medication therapy and its reason for use will be presented by treatment group and overall for SAF.

7.3 Study Drugs

7.3.1 Exposure

The following information on drug exposure will be presented for each treatment regimen for the SAF:

- Descriptive statistics for cumulative amount of the drug subject was exposed to and actual dose intensity; and
- Number and percent of subject with dose adjustments or interruptions and reasons for dose adjustments and interruptions by treatment regimen.

7.3.2 Relative Dose Intensity

RDI will be examined for subjects in the SAF whose total study drug count and first and last days of treatment are known.

RDI will be summarized in two ways for the SAF:

- Descriptive statistics will be presented by treatment regimen.
- RDI will be categorized according to the following categories by treatment regimen:
 - o less than 50%
 - o at least 50%, less or equal to 80%
 - o greater than 80%
 - Unknown.

7.4 Analysis of Efficacy

Efficacy analyses will be conducted on the FAS and PPS. The interpretation of results from statistical tests will be based on the FAS. The PPS will be used to assess the robustness of the results from the statistical tests based on the FAS. All randomized subjects will be analyzed according to the treatment to which they are randomized.

7.4.1 Analysis of Primary Endpoint

The primary analysis will be performed on progression-free survival as assed by the IRR (PFS#1) on the FAS. In order to compare the PFS#1 between ASP8273 and the comparator Erlotinib/Gefitinib, the null hypothesis will be constructed:

• H₀₁: PFS of ASP8273 is not better than the comparator erlotinib/gefitinib

The accompanying alternative hypothesis is:

• H₁₁: PFS of ASP8273 is better than the comparator erlotinib/gefitinib

The primary analysis will be performed when approximately 362 PFS#1 events have been observed. Comparison of ASP8273 and erlotinib/gefitinib will be tested at 1-sided significance level of 0.025.

The distribution of PFS will be estimated for each treatment arm using Kaplan-Meier methodology and compared between Arm A and Arm B using log-rank test stratified by ECOG PS (0 and 1 combined versus 2), EGFR mutation type (exon 19 vs exon 21), and TKI chosen (erlotinib versus gefitinib). In addition, stratified Cox proportional hazard model will be used to estimate the hazard ratio and the corresponding 95% confidence interval.

The sensitivity analyses for PFS include:

- The primary analysis repeated for PPS
- The primary analysis including clinical progression as an event may be performed on the FAS
- If there is a difference in the stratification values between IRT and the CRF, primary analysis may be repeated on the FAS using CRF stratification values

Sponsor: Astellas Pharma Global Development, Inc.

ISN/Protocol 8273-CL-0302

• PFS#1 as assessed by the IRR will be analyzed using restricted mean survival time (RMST) approach from time 0 to 36 months. The restricted mean is a measure of average survival from time 0 to a specified timepoint. This approach does not require any model assumptions such as proportional hazards.

Table 4 PFS#1 Definition

Situation	Date of Event or Censor	Outcome			
No evaluable post-baseline imaging assessments, no death	Date of randomization	Censor			
Subject did not receive new anti-cancer therapy:					
Radiographical progression documented per RECIST v1.1	Date of radiological PD	Event			
No radiographical progression, but death recorded on eCRF	Date of death	Event			
No radiographical progression nor death	Date of last radiological assessment or at the date of randomization if no post-baseline radiological assessment is available	Censor			
Subject received new anti-cancer (ACT)	therapy:				
Radiographical progression documented per RECIST v1.1 after new ACT	Date of last radiological assessment before start of new anti-cancer therapy or at the date of randomization if no post-baseline radiological assessment is available	Censor			
Radiographical progression documented per RECIST v1.1 before new ACT	Date of radiological PD	Event			
No radiographical progression before new ACT but death recorded	Date of last radiological assessment before start of new anti-cancer therapy or at the date of randomization if no post-baseline radiological assessment is available	Censor			
No radiographical progression nor death	Date of last radiological assessment before start of new anti-cancer therapy or at the date of randomization if no post-baseline radiological assessment is available	Censor			
Missed 2 scheduled radiological assessm	ents:				
If radiographical progression or death occurs after missing 2 scheduled radiological assessments	Date of last radiological assessment or at the date of randomization if no post-baseline radiological assessment is available	Censor			

PFS#1 = Date of Event or Censor – Date of Randomization +1

In addition, since it is likely that K-M curves of PFS#1 as assessed by IRR will separate late in the study, Harrington-Fleming test will be performed as exploratory analysis with prespecified weight of p=0 and q=0.5. Different weights may be used as well.

Sponsor: Astellas Pharma Global Development, Inc.

ISN/Protocol 8273-CL-0302

To investigate non-proportionality between the treatment arms, the LOG(–LOG) survivor function versus time curves will be plotted. The scaled Schoenfeld residuals by time plot will be examined for evidence of a non-zero correlation, which indicates non-proportionality. Piecewise Cox models may be explored given evidence of non-proportional hazards.

Hochberg procedure will be used to control the overall error rate at 1-sided 0.025 level for the secondary efficacy endpoints (OS and ORR). Only when the primary endpoint significantly favors the ASP8273 arm will secondary endpoints be tested.

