7.1 Sample Size

Approximately 600 subjects will be randomized in a 1:1 ratio to 2 treatment arms: Arm A (ASP8273) and Arm B (erlotinib or gefitinib). Randomization will be stratified by ECOG PS (0, 1 or 2), EGFR mutation type (exon 19 deletion or mutation in exon 21 [L858R]), TKI chosen (erlotinib versus gefitinib) and race (Asian versus nonAsian). Assuming HR=0.667 (median PFS in Arm A and Arm B are 15.6 months and 10.4 months, respectively), a total of 420 PFS events will provide approximately 98.7% power to detect a statistically significant difference at type I error rate of 1-sided 0.025.

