7.4.1 Analysis of Primary Endpoint

7.4.1.1 Primary Analysis

The primary endpoint is PFS assessed by the blinded IRR. For each subject, PFS is defined as the time from the date of randomization until the date of radiological disease progression (i.e., PFS#1) assessed by IRR, or until death due to any cause. If a subject has neither progressed nor died, the subject will be censored at the date of last radiological assessment. Subjects who receive any further anticancer therapy for the disease before radiological progression will be censored at the date of the last radiological assessment before the anticancer therapy started. If progression or death occurs after missing 2 scheduled radiological assessments, the subject will be censored at the date of last radiological assessment or at the date of randomization if no postbaseline radiological assessment is available.

The primary analysis will be performed when approximately 420 PFS#1 events have been observed.

The distribution of PFS will be estimated for each treatment arm using Kaplan-Meier methodology and compared between Arm A and Arm B using log-rank test stratified by ECOG PS (0 and 1 combined versus 2), EGFR mutation type, and TKI chosen (erlotinib versus gefitinib). In addition, stratified Cox proportional hazard model will be used to estimate the hazard ratio and the corresponding 95% confidence interval.

The primary analysis will be performed using the FAS.

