Following discontinuation from study drug, subjects will have a follow-up visit within 30 days after their last dose of drug for safety assessments. If a subject discontinues study drug prior to radiographic disease progression (i.e., PFS#1), the subject should enter the post-treatment follow-up period and continue to undergo imaging assessments every 56 days (+/- 7 days) until PFS#1 is documented or the subject starts another anticancer treatment, whichever occurs earlier.

Following PFS#1, subjects will enter the long-term follow-up period and be followed every 3 months from the date of the follow-up visit for survival status and progression status on subsequent therapy (i.e., PFS#2). All subsequent anticancer therapy including date and site of progression for PFS#2 will be recorded on the case report form. Subjects will be followed until PFS#2 is documented such as investigator-determined progression, death, subject has ended the subsequent anticancer therapy or the subject starts another anticancer treatment, whichever occurs earlier.

Following PFS#2, subjects will enter the survival follow-up period and be followed every 3 months for survival status.

Samples for pharmacokinetics, biomarkers and pharmacogenomics (PGx) as well as formalin fixed paraffin embedded (FFPE) specimens for central analysis will be collected. Eligibility may be determined by a previously documented EGFR mutation result. However, there should be sufficient tissue from the specimen used to generate the EGFR test result to send to the central lab for confirmatory testing. If a subject does not have a previously documented EGFR mutation test result, then a fresh specimen must be obtained and sent to the central lab for eligibility testing. From initial progression (PFS#1), an optional post-progression tumor tissue sample for exploratory biomarker analysis may be collected following centrally confirmed disease progression for subjects who sign a separate informed consent form (ICF).

An independent Data Monitoring Committee (IDMC) will be chartered to oversee safety and the planned futility analysis which will occur after at least 210 PFS events have been observed.

The primary analysis will occur when at least 420 PFS#1 events are observed which is expected to occur approximately 36 months after randomization. Primary endpoint, secondary endpoints and other endpoints will be analyzed at the time of primary analysis.

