4 SAMPLE SIZE

Approximately 600 subjects will be randomized in a 1:1 ratio to 2 treatment arms: Arm A (ASP8273) and Arm B (erlotinib or gefitinib). Randomization will be stratified by ECOG PS (0, 1 or 2), EGFR mutation type (exon 19 deletion or mutation in exon 21 [L858R]), TKI chosen (erlotinib versus gefitinib) and race (Asian versus non-Asian). Assuming HR=0.667 (median PFS in Arm A and Arm B are 15.6 months and 10.4 months, respectively), a total of 420 PFS events will provide approximately 95% power to detect a statistically significant difference at type I error rate of 1-sided 0.025.

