8 DOCUMENT REVISION HISTORY

Version	Date	Changes	Comment/rationale for change
1.0	02-Oct-2015	NA	Document finalized
2.0	24-Jun-2016	Section 2: Flow chart Table 1 and Table 2: Schedule of assessment Sections 3.1.2, 3.1.3 and 3.2.1 - Quality of Life (QoL) was moved from an exploratory to a secondary endpoint. Section 4 - Sample size and number of events required was changed to 600 and 420, respectively.	Changes were made to align the SAP with the protocol version 2.0
		Section 7.10 - Updated the sample size and the number of events required for the interim analysis	
		Section 6.6 Provided additional text on how to handle duration variables when the date is incomplete or missing Added definition of previous and concomitant non-medication therapy	To clarify the rule in duration derivation when dates are incomplete or missing and also clarify the definition of previous and concomitant non-medication therapy.
		Section 7.1 Provided additional text in derivation of study day and baseline	To provide guidance on how to derive study day and baseline since different reference date will be used for safety and efficacy assessments
		Section 7.4.1 Added sensitivity analysis and exploratory analysis to the primary endpoint (PFS#1 as assessed by IRR)	Late separation of survival curves is expected to occur
		Section 7.4.1.1 Added sensitivity analysis and exploratory analysis to overall survival	To investigate the potential effect of subsequent therapies on overall survival
		Section 7.5.1 Added additional summaries for adverse events	Adverse events leading to dose reduction and drug interruptions are important safety information
		Section 7.5.7 Added text in time to deterioration derivation	Provided clarification regarding the reference date to be used for time to deterioration

Version	Date	Changes	Comment/rationale for
			change
		Section 7.2.4	Concomitant medications will
		Added a text to clarify the coding	be coded by indication-specific
		process for concomitant medication	ATC
		Section 7.2.8	Added section on how to
		New section for previous and	summarize previous and
		concomitant non-medication therapy	concomitant non-medication
			therapy

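### SAP 7.4.1 triggers the primary PFS analysis at about 362 events; the rest of the SAP and the protocol say 420

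*SAP*

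**What the plan says.** SAP 7.4.1 sets out the hypotheses, the one-sided 0.025 level, the stratified log-rank test and the censoring table for PFS by independent review. Its timing sentence reads: "The primary analysis will be performed when approximately 362 PFS#1 events have been observed".

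The other current statements are:

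- SAP 3.2.1: "The primary analysis will occur when at least 420 PFS#1 events are observed". Protocol 2.2.1 and the protocol synopsis give the same count.
- SAP 4: "420 PFS events will provide approximately 95% power".
- Protocol 7.1: "420 PFS events will provide approximately 98.7% power".
- Protocol 7.4.1.1, the direct counterpart of the SAP sentence: "The primary analysis will be performed when approximately 420 PFS#1 events have been observed".
- SAP 7.9 and Protocol 7.9: the futility look comes at 210 events, half of 420.

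The SAP revision history (Section 8) presents version 2.0 as aligned with protocol version 2.0. Its entry for Section 4 reads: "Sample size and number of events required was changed to 600 and 420, respectively". Its entry for Section 7.4.1 mentions no event count: "Added sensitivity analysis and exploratory analysis to the primary endpoint". Attachment 1 of the protocol shows 362 as the pre-amendment target, struck out and replaced by 420.

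**The concern.** The event count decides when the data are cut for the one confirmatory test, and a significant PFS result is also the gate to testing OS and ORR. The two counts are too far apart for the word approximately to cover both. Someone programming the analysis from SAP 7.4.1 would cut at 362; someone working from SAP 3.2.1 or the protocol would wait for 420. Neither document has a formal rule of precedence.

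The difference bears on the purpose of the amendment. Amendment 1 raised the sample size, and the event counts with it, to protect power if the PFS curves separate late in what it describes as the single pivotal study. SAP 7.4.1 itself states that "it is likely that K-M curves of PFS#1 as assessed by IRR will separate late". Stopping at 362 would discard the late follow-up that the amendment was meant to secure.

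**Working it through.** **Inputs.** Hazard ratio 0.667 from medians of 15.6 and 10.4 months, one-sided alpha 0.025, 1:1 allocation, about 600 subjects (Protocol 7.1, SAP 4). Candidate triggers d = 420 and d = 362. Timing anchors: 210 events at about month 22 (Protocol 7.9) and 420 at about month 36 (Protocol 2.2.1).

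**1. Reproduce the protocol's power.** Schoenfeld: power = Φ(√d/2 × |ln HR| − 1.96), with |ln 0.667| = 0.405.

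- d = 420: √420/2 = 10.247; 10.247 × 0.405 − 1.96 = 2.19; power = 98.6%. This agrees with the stated 98.7%. Freedman's formula gives 98.4%.

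**2. Apply the same formula to the SAP 7.4.1 count.**

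- d = 362: √362/2 = 9.513; 9.513 × 0.405 − 1.96 = 1.89; power = 97.1% (Freedman 96.7%).

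**3. Observed hazard ratio needed for significance**, exp(−1.96 × 2/√d): 0.826 at 420 and 0.814 at 362.

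**4. Shortfall and interim fraction.** 420 − 362 = 58 events, and 58/420 = 13.8%. The 210-event futility look falls at 210/420 = 50% of the information, or 210/362 = 58%.

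**5. SAP 4's 95%.** Step 1 gives 98.6% at 420 events. Solving the same formula for 95% gives d = 4 × (1.96 + 1.645)²/0.405² ≈ 317 events. The pre-amendment protocol paired 95% with 362 events, so this too looks like a leftover.

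**6. How much earlier the cut would fall.** The documents give neither accrual period nor dropout rate, so these are estimates.

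- Average rate between the anchors: (420 − 210)/(36 − 22) = 15 events per month; 58/15 = 3.9 months.
- Exponential PFS with the planned medians and uniform accrual, with the accrual length solved so that 420 events are expected at month 36:

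| Assumed dropout per year | Accrual (months) | 362 events at month | Months early | 210 events at month |
|---|---|---|---|---|
| 0% | 24.8 | 30.8 | 5.2 | 21.2 |
| 5% | 21.5 | 29.8 | 6.2 | 19.8 |
| 10% | 17.0 | 28.3 | 7.7 | 17.4 |

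The no-dropout case fits the documented month 22 best (223 events expected then). The fit worsens as dropout rises.

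**7. Late separation, as an illustration.** Log-rank simulation (40,000 runs, unstratified, uniform accrual over 24.8 months). The arms share one hazard up to the delay; afterwards the ASP8273 hazard is set so that its median stays at 15.6 months. The delay lengths are assumed.

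| Delay (months) | Hazard ratio after delay | Power at 362 | Power at 420 |
|---|---|---|---|
| 0 (check) | 0.667 | 97% | 98.5% |
| 3 | 0.587 | 94% | 98% |
| 4 | 0.552 | 92% | 98% |
| 6 | 0.458 | 90% | 98% |

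**The case against.** The strongest reply is that nobody could seriously doubt which number is meant. The SAP describes itself as elaborating the protocol, its log says that version 2.0 was aligned with protocol 2.0, the protocol's counterpart sentence says 420, and the interim sits at exactly half of 420. That is right, and it makes this a stale number and not an open design choice. It does not make the operative sentence correct.

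The revision log is also weak evidence of how the error arose. Its entry for 3.2.1 mentions only the quality-of-life change although that section now carries 420, and it files the interim update under 7.10 when the text is in 7.9. The case that 362 is superseded therefore rests on the protocol amendment, which is sufficient.

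On size, the loss under the planned effect is 1.5 points of power with alpha unchanged. The larger losses depend on delays and post-delay effects that the documents do not give. If the hazard ratio after the delay is held at 0.667 instead, power is about 64% against 77% for a 4-month delay and 42% against 59% for 6 months. Those gaps are wider, so the table is not a worst case, but it is one scenario and not a range that the documents support.

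Finally, SAP 7.10.4 and Appendix 2 keep treatment codes from the study statisticians and programmers until database lock. This limits any data-driven choice between the two counts. It limits it only in part: the trial is open-label, and other team members may see individual assignments.

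**Conclusion.** The point holds: SAP 7.4.1 carries a superseded event count for the primary analysis and must be corrected. The evident intention is 420. Following 362 would cost 58 events (13.8%) and 1.5 points of power if hazards are proportional at 0.667. It would cost more under late separation: about 4 to 8 points in the scenarios that keep the planned medians. The cut would come about 5 months early without dropout; the range of about 4 to 8 months rests on assumed dropout, and its upper end fits the documented interim timing poorly. The correction is required because the wrong number sits in the rule for the confirmatory test; the power loss under the planned effect would not by itself demand it. The 95% power in SAP 4 is a second, smaller error: it does not affect the trigger, but it contradicts Protocol 7.1 and does not reproduce.

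**What to change.** In SAP 7.4.1, replace 362 with 420 PFS#1 events assessed by independent review. In SAP 4, change 95% to the 98.7% of Protocol 7.1. Record both changes in SAP Section 8, and finalise the revision before the data cut-off.

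Optionally, settle on one wording: SAP 3.2.1 and Protocol 2.2.1 set 420 as a minimum, while Protocol 7.4.1.1 gives it as an approximation. The SAP can state which governs, and the protocol wording can wait for its next amendment.

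The cost is two figures and a log entry. There are no additional patients and no change to the design.
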